9.3. Programming Conventions

- Page orientation, margins, and fonts: Summary tables, listings, and figures will appear in landscape orientation. There should be a 1.0" boundary on the left and right edges. The top and bottom margins are 1.0" for tables and listings but may vary for figures. Output should be printed in Courier New with a point size of 8.
- Identification of analysis population: Every summary table and figure will clearly specify the analysis population being summarized. Listings will be prepared for all subjects randomized.
- Group headers: In the summary tables, the group headers will identify the within-group sample size for the indicated analysis population. Of note, the header's sample size does not necessarily equal the number of subjects actually summarized within any given summary module; some subjects in the analysis population may have missing values and thus may not be summarized.
- Suppression of percentages corresponding to null categories: When count data are presented as category frequencies and corresponding percentages, the percent should be suppressed when the count is zero in order to draw attention to the non-zero counts.
- Presentation of sample sizes: Summary modules should indicate, in one way or another, the number of subjects actually contributing to the summary statistics presented in any given summary module. As mentioned above, this may be less than the number of subjects in the analysis population.
 - In the quantitative modules describing continuous variables (and thus presenting sample size, means, and standard deviations), the sample size should be the number of non-missing observations
 - For categorical variables that are presented in frequency tables, the module should present the total count in addition to the count in each category. Percentages should be calculated using this total as the denominator, and the percentage corresponding to the sum itself (that is, 100%) should be presented so as to indicate clearly to a reviewer the method of calculation.
- Sorting: Listings will be sorted by subject number and date, if applicable. If a listing is sorted in a different manner, it will be indicated on the listing shells.
- General formatting rules: Rounding for all variables will occur only as the last step, immediately prior to presentation in listings, tables, and figures. No intermediate rounding will be performed on derived variables. The standard rounding practice of rounding numbers ending in 0-4 down and numbers ending in 5-9 up will be employed.
- Numerical Values: The presentation of numerical values will adhere to the following guidelines:
 - Raw measurements will be reported to the number of significant digits as captured electronically or on the CRFs.

- Standard deviations will be reported to two decimal places beyond the number of decimal places the original parameter is presented.
- Means and quartiles will be reported to one decimal place beyond the number of decimal places the original parameter is presented.
- Calculated percentages will be reported with one decimal.
- Coefficient of variation will be reported to the same number of decimal places as the standard deviation.
- Dates will be formatted as DDMMYY YYYY. Partial dates will be presented on data listings as recorded on CRFs.
- Time will be presented according to the 24-hour clock (HH:MM).
- Verification of Results: All analyses will be subject to formal verification procedures. Specifically, results will be verified utilizing independent programming prior to issuance of the draft statistical report. All documents will be verified by the lead statistician to ensure accuracy and consistency of analyses.

9.4. CTCAE Based Laboratory Test Results Grading Specifications

Lab Test = Albumin

CTCAE Term	Grade 1	Grade 2	Grade 3	Grade 4	Grade 5
Hypoalbuminemia	<LLN - 3 g/dL; <LLN - 30 g/L	<3 - 2 g/dL; <30 - 20 g/L	<2 g/dL; <20 g/L	Life-threatening consequences; urgent intervention indicated	Death

Albumin will have grades 1-3,

- Grade 1 being any values from the LLN to 3 g/dL,
- Grade 2 from 2 to < 3 g/dL and
- Grade 3 < 2 g/dL

Lab Test = Amylase

CTCAE Term	Grade 1	Grade 2	Grade 3	Grade 4	Grade 5
Serum amylase increased	>ULN - 1.5 x ULN	>1.5 - 2.0 x ULN; >2.0 - 5.0 x ULN and asymptomatic	>2.0 - 5.0 x ULN with signs or symptoms; >5.0 x ULN and asymptomatic	>5.0 x ULN and with signs or symptoms	-

Amylase will have Grades 1, 2 and 3:

- Grade 1 being any values from the ULN to 1.5 x ULN
- Grade 2 from >1.5 to 5.0 x ULN
- Grade 3 from >5 x ULN

Lab Test = Alkaline Phosphatase

CTCAE Term	Grade 1	Grade 2	Grade 3	Grade 4	Grade 5
Alkaline phosphatase increased	>ULN - 2.5 x ULN if baseline was normal; 2.0 - 2.5 x baseline if baseline was abnormal	>2.5 - 5.0 x ULN if baseline was normal; >2.5 - 5.0 x baseline if baseline was abnormal	>5.0 - 20.0 x ULN if baseline was normal; >5.0 - 20.0 x baseline if baseline was abnormal	>20.0 x ULN if baseline was normal; >20.0 x baseline if baseline was abnormal	-

Alkaline Phosphatase will have grades 1-4 and grading is based ULN only.

- Grade 1 being any values from the ULN to 2.5 x ULN
- Grade 2 from >2.5 to 5.0 x ULN
- Grade 3 from >5.0 to 20.0 x ULN
- Grade 4 from >20.0 x ULN

Lab Test = Alanine Aminotransferase

CTCAE Term	Grade 1	Grade 2	Grade 3	Grade 4	Grade 5
Alanine aminotransferase increased	>ULN - 3.0 x ULN if baseline was normal; 1.5 - 3.0 x baseline if baseline was abnormal	>3.0 - 5.0 x ULN if baseline was normal; >3.0 - 5.0 x baseline if baseline was abnormal	>5.0 - 20.0 x ULN if baseline was normal; >5.0 - 20.0 x baseline if baseline was abnormal	>20.0 x ULN if baseline was normal; >20.0 x baseline if baseline was abnormal	-

ALT will have grades 1-4 and grading is based ULN only. The baseline abnormality will be ignored.

- Grade 1 being any values from the ULN to 3.0 x ULN
- Grade 2 from >3.0 to 5.0 x ULN
- Grade 3 from >5.0 to 20.0 x ULN
- Grade 4 from >20.0 x ULN

Lab Test = Aspartate Aminotransferase

CTCAE Term	Grade 1	Grade 2	Grade 3	Grade 4	Grade 5
Aspartate aminotransferase increased	>ULN - 3.0 x ULN if baseline was normal; 1.5 - 3.0 x baseline if baseline was abnormal	>3.0 - 5.0 x ULN if baseline was normal; >3.0 - 5.0 x baseline if baseline was abnormal	>5.0 - 20.0 x ULN if baseline was normal; >5.0 - 20.0 x baseline if baseline was abnormal	>20.0 x ULN if baseline was normal; >20.0 x baseline if baseline was abnormal	-

AST will have grades 1-4 and grading is based ULN only.

- Grade 1 being any values from the ULN to 3.0 x ULN
- Grade 2 from >3.0 to 5.0 x ULN
- Grade 3 from >5.0 to 20.0 x ULN
- Grade 4 from >20.0 x ULN

Lab Test = Bilirubin

CTCAE Term	Grade 1	Grade 2	Grade 3	Grade 4	Grade 5
Blood bilirubin increased	>ULN - 1.5 x ULN if baseline was normal; >1.0 - 1.5 x baseline if baseline was abnormal	>1.5 - 3.0 x ULN if baseline was normal; >1.5 - 3.0 x baseline if baseline was abnormal	>3.0 - 10.0 x ULN if baseline was normal; >3.0 - 10.0 x baseline if baseline was abnormal	>10.0 x ULN if baseline was normal; >10.0 x baseline if baseline was abnormal	-

Bilirubin will have grades 1-4 and grading is based ULN only

- Grade 1 being any values from the ULN to 1.5 x ULN
- Grade 2 from >1.5 to 3.0 x ULN
- Grade 3 from >3.0 to 10.0 x ULN
- Grade 4 from >10.0 x ULN

Lab Test = Corrected Serum Calcium

CTCAE Term	Grade 1	Grade 2	Grade 3	Grade 4	Grade 5
Hypocalcemia	Corrected serum calcium of <LLN - 8.0 mg/dL; <LLN - 2.0 mmol/L; Ionized calcium <LLN - 1.0 mmol/L	Corrected serum calcium of <8.0 - 7.0 mg/dL; <2.0 - 1.75 mmol/L; Ionized calcium <1.0 - 0.9 mmol/L; symptomatic	Corrected serum calcium of <7.0 - 6.0 mg/dL; <1.75 - 1.5 mmol/L; Ionized calcium <0.9 - 0.8 mmol/L; hospitalization indicated	Corrected serum calcium of <6.0 mg/dL; <1.5 mmol/L; Ionized calcium <0.8 mmol/L; life-threatening consequences	Death
Hypercalcemia	Corrected serum calcium of >ULN - 11.5 mg/dL; >ULN - 2.9 mmol/L; Ionized calcium >ULN - 1.5 mmol/L	Corrected serum calcium of >11.5 - 12.5 mg/dL; >2.9 - 3.1 mmol/L; Ionized calcium >1.5 - 1.6 mmol/L; symptomatic	Corrected serum calcium of >12.5 - 13.5 mg/dL; >3.1 - 3.4 mmol/L; Ionized calcium >1.6 - 1.8 mmol/L; hospitalization indicated	Corrected serum calcium of >13.5 mg/dL; >3.4 mmol/L; Ionized calcium >1.8 mmol/L; life-threatening consequences	Death

Calcium will have to be corrected for albumin using the formula previously discussed (NOTE: It should be confirmed with the lab whether or not the correction has already been applied). The grading is in both directions High and Low. Both directions are graded in 4 categories as Hypercalcemia

- Grade 1 being any values from the ULN to 11.5 mg/dL,
- Grade 2 from >11.5 to 12.5 mg/dL,
- Grade 3 from >12.5 to 13.5 mg/dL,
- Grade 4 >13.5 mg/dL

Hypocalcemia

- Grade 1 being any values from the LLN to 8.0 mg/dL,
- Grade 2 from 7.0 to <8.0 mg/dL,
- Grade 3 from 6.0 to <7.0 mg/dL,
- Grade 4 <6.0 mg/dL

Lab Test = Cholesterol

CTCAE Term	Grade 1	Grade 2	Grade 3	Grade 4	Grade 5
Cholesterol high	>ULN - 300 mg/dL; >ULN - 7.75 mmol/L	>300 - 400 mg/dL; >7.75 - 10.34 mmol/L	>400 - 500 mg/dL; >10.34 - 12.92 mmol/L	>500 mg/dL; >12.92 mmol/L	-

Cholesterol will have grades 1-4,

- Grade 1 being any values from the ULN to 300 mg/dL,
- Grade 2 from >300 to 400 mg/dL,
- Grade 3 from >400 to 500 mg/dL,
- Grade 4 >500 mg/dL

Lab Test = Creatine Kinase

CTCAE Term	Grade 1	Grade 2	Grade 3	Grade 4	Grade 5
CPK increased	>ULN - 2.5 x ULN	>2.5 x ULN - 5 x ULN	>5 x ULN - 10 x ULN	>10 x ULN	-

Creatine Kinase will have grades 1-4,

- Grade 1 being any values from the ULN to 2.5 x ULN,
- Grade 2 from >2.5 to 5 x ULN,
- Grade 3 from >5 to 10 x ULN,
- Grade 4 >10 ULN

Lab Test = Creatinine

CTCAE Term	Grade 1	Grade 2	Grade 3	Grade 4	Grade 5
Creatinine increased	>ULN - 1.5 x ULN	>1.5 - 3.0 x baseline; >1.5 - 3.0 x ULN	>3.0 x baseline; >3.0 - 6.0 x ULN	>6.0 x ULN	-

Creatinine will have grades 1-4 and will be based on the baseline value in some cases. Grading for pre-baseline values will ignore the baseline requirement.

- Grade 1 being any values from the ULN to 1.5 x ULN,
- Grade 2 from >1.5 to 3.0 x ULN or >1.5 - 3.0 x baseline,
- Grade 3 from >3.0 to 6.0 x ULN or >3.0 x baseline,
- Grade 4 >6.0 x ULN

Lab Test = Fibrinogen

CTCAE Term	Grade 1	Grade 2	Grade 3	Grade 4	Grade 5
Fibrinogen decreased	<1.0 - 0.75 x LLN; if abnormal, <25% decrease from baseline	<0.75 - 0.5 x LLN; if abnormal, 25 - <50% decrease from baseline	<0.5 - 0.25 x LLN; if abnormal, 50 - <75% decrease from baseline	<0.25 x LLN; if abnormal, 75% decrease from baseline; absolute value <50 mg/dL	-

Fibrinogen will have Grades 1- 4:

- Grade 1 <1.0 - 0.75 x LLN
- Grade 2 <0.75 - 0.5 x LLN
- Grade 3 <0.5 - 0.25 x LLN
- Grade 4 <0.25 x LLN

Lab Test = Gamma-Glutamyl Transpeptidase

CTCAE Term	Grade 1	Grade 2	Grade 3	Grade 4	Grade 5
GGT increased	>ULN - 2.5 x ULN if baseline was normal; 2.0 - 2.5 x baseline if baseline was abnormal	>2.5 - 5.0 x ULN if baseline was normal; >2.5 - 5.0 x baseline if baseline was abnormal	>5.0 - 20.0 x ULN if baseline was normal; >5.0 - 20.0 x baseline if baseline was abnormal	>20.0 x ULN if baseline was normal; >20.0 x baseline if baseline was abnormal	-

Gamma-Glutamyl Transpeptidase will have grades 1-4 and based on ULN only

- Grade 1 being any values from the ULN to 2.5 x ULN,
- Grade 2 from >2.5 to 5.0 x ULN
- Grade 3 from >5.0 to 20.0 x ULN
- Grade 4 from >20.0 x ULN

Lab Test = Glucose

CTCAE Term	Grade 1	Grade 2	Grade 3	Grade 4	Grade 5
Hyperglycemia	Abnormal glucose above baseline with no medical intervention	Change in daily management from baseline for a diabetic; oral antiglycemic agent initiated; workup for diabetes	Insulin therapy initiated; hospitalization indicated	Life-threatening consequences; urgent intervention indicated	Death
Hypoglycemia	<LLN - 55 mg/dL; <LLN - 3.0 mmol/L	<55 - 40 mg/dL; <3.0 - 2.2 mmol/L	<40 - 30 mg/dL; <2.2 - 1.7 mmol/L	<30 mg/dL; <1.7 mmol/L; life-threatening consequences; seizures	Death

Glucose is graded in 2 directions.

Hypoglycemia will have grades 1-4,

- Grade 1 being any values from the LLN to 55 mg/dL,
- Grade 2 from 40 to <55 mg/dL,
- Grade 3 from 30 to <40 mg/dL,
- Grade 4 <30 mg/dL

Hyperglycemia will have one grade. We discussed using the WHO criterion as noted below

- Grade 1 >200 mg/dL;

Lab Test = Lipase

CTCAE Term	Grade 1	Grade 2	Grade 3	Grade 4	Grade 5
Serum lipase increased	>ULN - 1.5 x ULN	>1.5 - 2.0 x ULN; >2.0 - 5.0 x ULN and asymptomatic	>2.0 - 5.0 x ULN with signs or symptoms; >5.0 x ULN and asymptomatic	>5.0 x ULN and with signs or symptoms	-

Lipase will have Grades 1, 2 and 3:

- Grade 1 being any values from the ULN to 1.5 x ULN
- Grade 2 from >1.5 to 5.0 x ULN
- Grade 3 from >5 x ULN

Lab Test = Magnesium

CTCAE Term	Grade 1	Grade 2	Grade 3	Grade 4	Grade 5
Hypermagnesemia	>ULN - 3.0 mg/dL; >ULN - 1.23 mmol/L	-	>3.0 - 8.0 mg/dL; >1.23 - 3.30 mmol/L	>8.0 mg/dL; >3.30 mmol/L; life-threatening consequences	Death
Hypomagnesemia	<LLN - 1.2 mg/dL; <LLN - 0.5 mmol/L	<1.2 - 0.9 mg/dL; <0.5 - 0.4 mmol/L	<0.9 - 0.7 mg/dL; <0.4 - 0.3 mmol/L	<0.7 mg/dL; <0.3 mmol/L; life-threatening consequences	Death

Hypermagnesemia will have grades 1, 3, and 4,

- Grade 1 being any values from the ULN to 3.0 mg/dL,
- Grade 3 from >3.0 to 8.0 mg/dL,
- Grade 4 from >8.0 mg/dL

Hypomagnesemia will have grades 1 - 4,

- Grade 1 being any values from the LLN to 1.2 mg/dL,
- Grade 2 from 0.9 to <1.2 mg/dL,
- Grade 3 from 0.7 to <0.9 mg/dL,
- Grade 4 <0.7 mg/dL

Lab Test = Potassium

CTCAE Term	Grade 1	Grade 2	Grade 3	Grade 4	Grade 5
Hyperkalemia	>ULN - 5.5 mmol/L	>5.5 - 6.0 mmol/L; intervention initiated	>6.0 - 7.0 mmol/L; hospitalization indicated	>7.0 mmol/L; life-threatening consequences	Death
Hypokalemia	<LLN - 3.0 mmol/L	Symptomatic with <LLN - 3.0 mmol/L; intervention indicated	<3.0 - 2.5 mmol/L; hospitalization indicated	<2.5 mmol/L; life-threatening consequences	Death

Hyperkalemia will have grades 1-4,

- Grade 1 being any values from the ULN to 5.5 mmol/L,
- Grade 2 from >5.5 to 6.0 mmol/L,
- Grade 3 from >6.0 to 7.0 mmol/L,
- Grade 4 from >7.0 mmol/L

Hypokalemia will have grades 1, 3, and 4,

- Grade 1 being any values from the LLN to 3.0 mmol/L,
- Grade 3 from >2.5 to 3.0 mmol/L,
- Grade 4 <2.5 mmol/L

Lab Test = Sodium

CTCAE Term	Grade 1	Grade 2	Grade 3	Grade 4	Grade 5
Hypernatremia	>ULN - 150 mmol/L	>150 - 155 mmol/L; intervention initiated	>155 - 160 mmol/L; hospitalization indicated	>160 mmol/L; life- threatening consequences	Death
Hyponatremia	<LLN - 130 mmol/L	125-129 mmol/L and asymptomatic	125-129 mmol/L symptomatic; 120-124 mmol/L regardless of symptoms	<120 mmol/L; life- threatening consequences	Death

Hypernatremia will have grades 1-4,

- Grade 1 being any values from the ULN to 150 mmol/L,
- Grade 2 from >150 to 155 mmol/L,
- Grade 3 from >155 to 160 mmol/L,
- Grade 4 from >160 mmol/L

Hyponatremia will have grades 1-4,

- Grade 1 being any values from the LLN to 130 mmol/L,
- Grade 2 from 125 to <130 mmol/L,
- Grade 3 from 120 to <125 mmol/L,
- Grade 4 <120 mmol/L

Lab Test = Triglycerides

CTCAE Term	Grade 1	Grade 2	Grade 3	Grade 4	Grade 5
Hypertriglyceridemia	150 mg/dL - 300 mg/dL; 1.71 mmol/L - 3.42 mmol/L	>300 mg/dL - 500 mg/dL; >3.42 mmol/L - 5.7 mmol/L	>500 mg/dL - 1000 mg/dL; >5.7 mmol/L - 11.4 mmol/L	>1000 mg/dL; >11.4 mmol/L; life-threatening consequences	Death

Triglycerides will have grades 1-4,

- Grade 1 being any values from the 150 to 300 mg/dL,
- Grade 2 from >300 to 500 mg/dL,
- Grade 3 from >500 to 1000 mg/dL,
- Grade 4 from >1000 mmol/L

Lab Test = Uric Acid

CTCAE Term	Grade 1	Grade 2	Grade 3	Grade 4	Grade 5
Hyperuricemia	>ULN without physiologic consequences	-	>ULN with physiologic consequences	Life-threatening consequences	Death

- Do not grade based on CTCAE

Lab Test = Bicarbonate or CO2

CTCAE Term	Grade 1	Grade 2	Grade 3	Grade 4	Grade 5
Blood bicarbonate decreased	<LLN and no intervention initiated	-	-	-	-

Do not Grade based on CTCAE

Lab Test = Phosphorus or Phosphate

CTCAE Term	Grade 1	Grade 2	Grade 3	Grade 4	Grade 5
Hypophosphatemia	Laboratory finding only and intervention not indicated	Oral replacement therapy indicated	Severe or medically significant but not immediately life-threatening; hospitalization or prolongation of existing hospitalization indicated	Life-threatening consequences	Death
Hyperphosphatemia	Laboratory finding only and intervention not indicated	Noninvasive intervention indicated	Severe or medically significant but not immediately life-threatening; hospitalization or prolongation of existing hospitalization indicated	Life-threatening consequences; urgent intervention indicated (e.g., dialysis)	Death

Do not Grade based on CTCAE

Lab Test = Serum pH [This is not urine pH]

CTCAE Term	Grade 1	Grade 2	Grade 3	Grade 4	Grade 5
Acidosis	pH <normal, but >=7.3	-	pH <7.3	Life-threatening consequences	-
Alkalosis	pH >normal, but <=7.5	-	pH >7.5	Life-threatening consequences	-

Serum pH will be graded in both directions with Grades 1 and 3 only.

Acidosis Grade 1.<LLN, but >=7.3 Grade 3, pH < 7.3

Alkalosis Grade 1.>ULN, but <=7.5 Grade 3, pH < 7.5

Lab Test = Activated Partial Thromboplastin Time

CTCAE Term	Grade 1	Grade 2	Grade 3	Grade 4	Grade 5
Activated partial thromboplastin time prolonged	>ULN - 1.5 x ULN	>1.5 - 2.5 x ULN	>2.5 x ULN; bleeding	-	-

APTT will have grades 1-3

- Grade 1 being any values from the >ULN to 1.5 x ULN,
- Grade 2 from >1.5 to 2.5 x ULN,
- Grade 3 from >2.5 x ULN,

Lab Test = International Normalized Ratio

CTCAE Term	Grade 1	Grade 2	Grade 3	Grade 4	Grade 5
INR increased	>1.2 - 1.5; >1 - 1.5 x baseline if on anticoagulation; monitoring only indicated	>1.5 - 2.5; >1.5 - 2.5 x baseline if on anticoagulation; dose adjustment indicated	>2.5; >2.5 x baseline if on anticoagulation; bleeding	-	-

INR will have grades 1-3

- Grade 1 being any values from the >1.2 to 1.5,
- Grade 2 from >1.5 to 2.5,
- Grade 3 from >2.5,

Lab Test = Eosinophils

CTCAE Term	Grade 1	Grade 2	Grade 3	Grade 4	Grade 5
Eosinophilia	>ULN and >Baseline	-	Steroids initiated	-	-

Do not grade based on CTCAE

Lab Test = Hemoglobin

CTCAE Term	Grade 1	Grade 2	Grade 3	Grade 4	Grade 5
Anemia	Hemoglobin (Hgb) <LLN - 10.0 g/dL; <LLN - 6.2 mmol/L; <LLN - 100 g/L	Hgb <10.0 - 8.0 g/dL; <6.2 - 4.9 mmol/L; <100 - 80g/L	Hgb <8.0 g/dL; <4.9 mmol/L; <80 g/L; transfusion indicated	Life-threatening consequences; urgent intervention indicated	Death
Hemoglobin Increased	Increase in > 0-2	Increase in >2-4g/dL	Increase > 4 g/DL	-	Death

Decreased Hemoglobin will have grades 1-3, with

- Grade 1 being any values from the LLN to 10 g/dL,
- Grade 2 from 8 to < 10 g/dL and
- Grade 3 < 8 g/dL

Increased Hemoglobin will not be graded.

Lab Test = CD4 Lymphocytes

CTCAE Term	Grade 1	Grade 2	Grade 3	Grade 4	Grade 5
CD4 lymphocytes decreased	<LLN - 500/mm3; <LLN - 0.5 x 10e9 /L	<500 - 200/mm3; <0.5 - 0.2 x 10e9 /L	<200 - 50/mm3; <0.2 x 0.05 - 10e9 /L	<50/mm3; <0.05 x 10e9 /L	-

Decreased CD4 count will have grades 1-4, with

- Grade 1 being any values from the LLN to 500/mm3,
- Grade 2 from <500 to 200/mm3 and
- Grade 3 from <200 to 50/mm3 and
- Grade 4 <50/mm3

Lab Test = Lymphocytes

CTCAE Term	Grade 1	Grade 2	Grade 3	Grade 4	Grade 5
Lymphocyte count decreased	<LLN - 800/mm ³ ; <LLN - 0.8 x 10 ⁹ /L	<800 - 500/mm ³ ; <0.8 - 0.5 x 10 ⁹ /L	<500 - 200/mm ³ ; <0.5 - 0.2 x 10 ⁹ /L	<200/mm ³ ; <0.2 x 10 ⁹ /L	Lymphocyte count decreased
Lymphocyte count increased	-	>4000/mm ³ - 20,000/mm ³	>20,000/mm ³	-	Lymphocyte count increased

Lymphocytes will be graded in both directions.

Decreased Lymphocytes will have grades 1-4, with

- Grade 1 being any values from the LLN to 800/mm³,
- Grade 2 from <800 to 500/mm³ and
- Grade 3 from <500 to 200/mm³ and
- Grade 4 <200/mm³

Increase Lymphocytes will have grades 2 and 3 only, with

- Grade 2 from >4000 to 20,000/mm³ and
- Grade 3 >20,000/mm³

Lab Test = Neutrophils

CTCAE Term	Grade 1	Grade 2	Grade 3	Grade 4	Grade 5
Neutrophil count decreased	<LLN - 1500/mm ³ ; <LLN - 1.5 x 10 ⁹ /L	<1500 - 1000/mm ³ ; <1.5 - 1.0 x 10 ⁹ /L	<1000 - 500/mm ³ ; <1.0 - 0.5 x 10 ⁹ /L	<500/mm ³ ; <0.5 x 10 ⁹ /L	-

Neutrophils will have grades 1-4, with

- Grade 1 being any values from the LLN to 1500/mm³,
- Grade 2 from 1000 to <1500/mm³ and
- Grade 3 from 500 to <1000/mm³ and
- Grade 4 <500/mm³

Lab Test = Platelets

CTCAE Term	Grade 1	Grade 2	Grade 3	Grade 4	Grade 5
Platelet count decreased	<LLN - 75,000/mm ³ ; - 75.0 x 10 ⁹ /L	<75,000 - 50,000/mm ³ ; <75.0 - 50.0 x 10 ⁹ /L	<50,000 - 25,000/mm ³ ; <50.0 - 25.0 x 10 ⁹ /L	<25,000/mm ³ ; <25.0 x 10 ⁹ /L	-

Do not grade with CTCAE.

Lab Test = WBC

CTCAE Term	Grade 1	Grade 2	Grade 3	Grade 4	Grade 5
White blood cell decreased	<LLN - 3000/mm3; <LLN - 3.0 x 10e9 /L	<3000 - 2000/mm3; <3.0 - 2.0 x 10e9 /L	<2000 - 1000/mm3; <2.0 - 1.0 x 10e9 /L	<1000/mm3; <1.0 x 10e9 /L	-
Leukocytosis	-	-	>100,000/mm3	Clinical manifestations of leucostasis; urgent intervention indicated	Death

Decreased WBC will have grades 1-4, with

- Grade 1 being any values from the LLN to 3000/mm3,
- Grade 2 from 2000 to <3,000/mm3 and
- Grade 3 from 1000 to <2,000/mm3 and
- Grade 4 <1000/mm3

High WBC will have grade 1, with

- Grade 1 >11,000/mm3 (<https://www.aafp.org/afp/2000/1101/p2053.html>),

Lab Test = Urine Glucose

CTCAE Term	Grade 1	Grade 2	Grade 3	Grade 4	Grade 5
Glucosuria	Present	-	-	-	-

Urine Glucose will have grade 1

- Grade 1 if not negative or trace

Lab Test = Urine Protein

CTCAE Term	Grade 1	Grade 2	Grade 3	Grade 4	Grade 5
Proteinuria	1+ proteinuria; urinary protein \geq ULN - <1.0 g/24 hrs	Adult: 2+ and 3+ proteinuria; urinary protein 1.0 - <3.5 g/24 hrs; Pediatric: Urine P/C (Protein/Creatinine) ratio 0.5 - 1.9	Adult: Urinary protein $\geq=3.5$ g/24 hrs; 4+ proteinuria; Pediatric: Urine P/C (Protein/Creatinine) ratio >1.9	-	-

Urine Protein will have grades 1-3, with

- Grade 1 =1+,
- Grade 2 = 2+ to 3+
- Grade 3 = 4+

Lab Test: Urine RBCs/Blood

CTCAE Term	Grade 1	Grade 2	Grade 3	Grade 4	Grade 5
Hematuria	Asymptomatic; clinical or diagnostic observations only; intervention not indicated	Symptomatic; urinary catheter or bladder irrigation indicated; limiting instrumental ADL	Gross hematuria; transfusion, IV medications, or hospitalization indicated; elective invasive intervention indicated; limiting self care ADL	Life-threatening consequences; urgent invasive intervention indicated	Death

Do not grade urine in blood using CTCAE

Lab Test: eGFR or CrCl

CTCAE Term	Grade 1	Grade 2	Grade 3	Grade 4	Grade 5
eGFR decreased/CrCl decreased	eGFR (estimated Glomerular Filtration Rate) or CrCl (creatinine clearance) <LLN - 60 ml/min/1.73 m ² or proteinuria 2+ present; urine protein/creatinine >0.5	eGFR or CrCl 59 - 30 ml/min/1.73 m ²	eGFR or CrCl 29 - 15 ml/min/1.73 m ²	eGFR or CrCl <15 ml/min/1.73 m ² ; dialysis or renal transplant indicated	Death

Values will be graded using the CTCAE values noted above with Grade 1 – Grade 4 values.

eGFR/CrCl:

Grade 1: < LLN – 60 ml/min/1.73 m²

Grade 2: 30 - < 60 ml/min/1.73 m²

Grade 3: 15 - < 30 ml/min/1.73 m²

Grade 4: < 15 ml/min/1.73 m²

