### **10.2 Appendix 2: Clinical Laboratory Tests**

The tests detailed in [Table 8](#) will be performed by the central laboratory.

Protocol-specific requirements for inclusion or exclusion of subjects are detailed in [Section 5](#).

Additional tests may be performed at any time during the trial as determined necessary by the investigator or required by local regulations.

Urine (serum tests to confirm any positive urine test) pregnancy tests are required for women of childbearing potential (WOCBP) at the time points indicated in the Schedule of Assessments; however, a serum pregnancy test can be done anytime during the trial at the investigator's discretion.

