**Table 8      Protocol-Required Safety Laboratory Assessments**

Laboratory Assessments	Parameters			
Hematology	Platelet Count	Red Blood Cell Indices: Mean Corpuscular Hemoglobin Mean Corpuscular Volume %Reticulocytes		White blood cell Count with Differential: Neutrophils Lymphocytes Monocytes Eosinophils Basophils
	Red blood cell Count			
	Hemoglobin			
	Hematocrit			
Clinical Chemistry	Blood urea nitrogen	Potassium	Aspartate Aminotransferase	Total and direct bilirubin
	Creatinine	Sodium	Alanine Aminotransferase	Total Protein
	Glucose	Calcium	Alkaline phosphatase	Chloride
	Bicarbonate			
Routine Urinalysis	Specific gravity pH, glucose, protein, blood, ketones, bilirubin, urobilinogen, nitrite, leukocyte esterase by dipstick Microscopic examination (if blood or protein is abnormal)			
Additional Required Tests	Urine drug screen for illicit drugs Urine dipstick pregnancy test (at time points indicated in Schedules of Assessments and as needed for women of childbearing potential), followed by serum pregnancy test if urine dipstick test is positive.			

Investigators must document their review of each laboratory safety report and file appropriately.

Laboratory results that could unblind the trial will not be reported to investigative sites or other blinded personnel until the trial has been unblinded.

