3.2.2. Clinical Safety Laboratory Assessments

The clinical laboratory tests as listed in the protocol will be performed in accordance with the laboratory manual and the Schedule of Assessments. All results, including repeats, will be included in the laboratory reports. The investigator must review the laboratory report, document this review, and record any clinically relevant changes occurring during the trial in the AE section of the eCRF.

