5.12.4. Clinical Laboratory Assessments

Descriptive summaries of selected (quantitative) clinical laboratory results and change from baseline will be presented by visit. Change from double-blind baseline will be summarized by visit. Additionally, for hematology, blood chemistry, coagulation, and urinalysis parameters, toxicity grade will be determined for laboratory tests with toxicity grade specified in [Section 9.4](#). Shifts from baseline to greatest (worst) treatment-emergent laboratory toxicity will be presented. For parameters not graded by CTCAE, laboratory values outside the normal range for each parameter will be identified using shift tables. Each subject's hematology, blood chemistry, and quantitative urinalysis values will be flagged as "low" (below the lower limit of normal/LLN), "normal" (within the normal range), or "high" (above the upper limit of normal/ULN) relative to the normal ranges of the central laboratory. In addition, the shift from baseline to the maximum post-baseline value and the minimum post-baseline value for each laboratory test.

The number and percentage of subjects who have post-baseline elevations in liver transaminase (alanine aminotransferase [ALT] or aspartate aminotransferase [AST]) or bilirubin abnormalities in relation to fold above the upper limit of normal will be summarized according to the Food and Drug Administration's Premarketing Clinical Evaluation on Drug-Induced Liver Injury Guidance for Industry ([FDA 2009](#)).

Abnormal hepatic laboratory values will be categorized and evaluated for any occurrence among all post-baseline assessments (where “and” in the bulleted list below indicates elevations occurring at the same visit). Within each laboratory parameter grouping, a subject may be counted once per elevation criteria using the worst-case result. That is, a subject with a worst case ALT elevation $> 5 \times$ the ULN would be counted once in the ALT $> 3 \times$ ULN category and once in the ALT $> 5 \times$ ULN category, regardless of how many ALT elevations the subject had that met the $> 5 \times$ ULN and $> 3 \times$ ULN elevation criteria.

- ALT and/or AST $> 3 \times$ ULN and total bilirubin > 1.5 or $2 \times$ ULN at the same visit at the same visit
- AST $> 3, 5, 10, 20 \times$ ULN
- ALT $> 3, 5, 10, 20 \times$ ULN
- Total bilirubin $> 1.5, 2 \times$ ULN
- Alkaline phosphatase (ALP) $> 1.5 \times$ ULN

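### The hypokalemia bounds in SAP 9.4 leave 2.5 mmol/L ungraded and put 3.0 mmol/L in two grades; secondarily, corrected calcium cannot be derived from the protocol-required panel

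*SAP*

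**What the plan says.** SAP 5.12.4 grades laboratory results by the rules in SAP 9.4 and then summarizes them: "Shifts from baseline to greatest (worst) treatment-emergent laboratory toxicity will be presented". For each test, section 9.4 prints a CTCAE row and, below it, the bullets to be programmed.

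**Potassium, low direction.** The bullets give Grade 1 from the LLN to 3.0 mmol/L, then "Grade 3 from >2.5 to 3.0 mmol/L", then Grade 4 below 2.5 mmol/L. The CTCAE row above them puts Grade 3 below 3.0 and down to 2.5, and Grade 4 below 2.5. The row's Grade 2 needs symptoms, and the bullets omit it.

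**Calcium.** The entry is for corrected serum calcium, and it instructs: "Calcium will have to be corrected for albumin using the formula previously discussed". A note follows: "It should be confirmed with the lab whether or not the correction has already been applied". Neither document prints a formula.

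**What is collected.** SAP 3.2.2 takes its tests from the protocol: "The clinical laboratory tests as listed in the protocol will be performed in accordance with the laboratory manual and the Schedule of Assessments". Protocol Table 8, "Protocol-Required Safety Laboratory Assessments", lists potassium and calcium. The nearest entry to albumin is "Total Protein"; albumin and ionized calcium are not listed.

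**The concern.** A grading rule should give every value below the LLN exactly one grade. The hypokalemia bullets fail this at two values that a laboratory can report, and they contradict the row they are meant to implement. At 2.5 mmol/L the failure hides a result that the row calls Grade 3. At 3.0 mmol/L the choice is between Grade 1 and Grade 3, with nothing between because the bullets have no Grade 2. Two programmers could resolve it differently.

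The calcium rule has a different problem: it needs an input and a formula that the documents do not provide. Calcium belongs to the required chemistry panel, and the schedules of assessments place a safety blood sample at all 17 numbered visits, so the gap would affect every subject's calcium grading.

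Laboratory changes are among the endpoints of the primary safety objective, and the worst-grade shift is one of their planned summaries.

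**Working it through.** The plan has no figure to reproduce here: the trial is descriptive and its sample size is not based on power. The check is whether each rule assigns exactly one grade.

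**Potassium inputs (SAP 9.4), k in mmol/L**

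- Bullets: Grade 1 if 3.0 ≤ k ≤ LLN; Grade 3 if 2.5 < k ≤ 3.0; Grade 4 if k < 2.5.
- CTCAE row, on the laboratory value alone: Grade 1 if 3.0 ≤ k < LLN; Grade 3 if 2.5 ≤ k < 3.0; Grade 4 if k < 2.5.
- Assumptions: results reported to one decimal; LLN = 3.5. The choice of LLN does not affect 2.5 or 3.0.

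| k (mmol/L) | SAP bullets | CTCAE row |
|---|---|---|
| 2.2 to 2.4 | 4 | 4 |
| **2.5** | **none** | **3** |
| 2.6 to 2.9 | 3 | 3 |
| **3.0** | **1 and 3** | **1** |
| 3.1 to 3.4 | 1 | 1 |
| 3.5 (assumed LLN) | 1 | none |

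The last line reflects only an inclusive reading of the LLN, a wording that other low-direction entries share. It is not pressed here.

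**Controls.** The same test on the hyponatremia bullets (118 to 135 mmol/L in steps of 1, LLN taken as 135) and the hypocalcemia bullets (5.5 to 8.5 mg/dL in steps of 0.1, LLN taken as 8.5) finds no gap and no overlap. Those entries keep the lower bound inside the grade: 125 to <130 for sodium Grade 2, 7.0 to <8.0 for calcium Grade 2. Hypomagnesemia (0.9 to <1.2) and hypoglycemia (40 to <55) are built the same way. The hypokalemia Grade 3 bullet has its inequality at the wrong end.

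**After correction.** With Grade 1 = 3.0 to <LLN, Grade 3 = 2.5 to <3.0 and Grade 4 = <2.5, the value 2.5 is Grade 3 only, 3.0 is Grade 1 only, and every value below the LLN has one grade.

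**Calcium: what the rule needs against what is listed**

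| Needed | In the documents |
|---|---|
| Total calcium | Yes, protocol Table 8 |
| Albumin | Not in Table 8 |
| Ionized calcium, the row's alternative measure | Not in Table 8 |
| Correction formula | Not printed in the protocol or SAP |

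Total protein does not stand in for albumin. Corrected calcium therefore cannot be derived from the required panel and the SAP as written.

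**The case against.** The strongest reply concerns calcium. Table 8 shows what is required, not everything the laboratory may report. The tests in it "will be performed by the central laboratory" under a laboratory manual that is not among these documents, protocol 10.2 allows additional tests, and the SAP itself leaves the correction to be confirmed with the laboratory. This stands in part. A reader might infer that albumin is never measured, that no one could make the correction, or that all calcium results are ungradable. The documents do not support any of these; they support only the limit set by the required panel. The reply does not complete the rule, however. A laboratory correction would itself need albumin, tests added at an investigator's discretion would not be systematic, and the formula is still missing. The albumin entry in section 9.4 does not show that albumin is collected, because the same appendix covers amylase, lipase, CD4 and INR, which are not in Table 8 either.

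For potassium, a reader might infer that every 3.0 would be reported as Grade 3 because the table takes the worst toxicity. SAP 5.12.4 does not say how to resolve one value that meets two definitions, so the result depends on how the rule is programmed. The grade at 3.0 is ambiguous; an error there is not established.

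It can also be said that the correct bounds are printed directly above and that SAP 9.3 requires independent programming. That may expose the overlap at 3.0. It need not expose the gap at 2.5, because two programmers who follow the bullets exactly would agree.

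Finally, clinically significant changes are judged by the investigator and recorded as adverse events (protocol 8.3.4), independently of these grades. This stands, and it limits the impact.

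**Conclusion.** The potassium rule is wrong as written. A 2.5 mmol/L receives no grade where the SAP's own row gives Grade 3, and a 3.0 mmol/L falls in Grades 1 and 3 together. That rests on the printed bounds alone; one-decimal reporting matters only for how often the two values occur.

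The calcium rule is an unfinished specification: its albumin input is not in the required panel and its formula is not stated. Whether the laboratory supplies albumin or corrected calcium cannot be settled from these documents.

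The consequence is small. The documents give no potassium distribution, so no count can be computed, but few results should fall exactly on 2.5 or 3.0. No hypothesis is tested. SAP 5.12.4 also flags each chemistry value as low, normal or high and plans shifts to the minimum and maximum post-baseline value. What is at risk is the toxicity grade, not the underlying result.

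**What to change.** **Potassium (SAP 9.4).** Replace the hypokalemia bullets with Grade 1 = 3.0 to <LLN, Grade 3 = 2.5 to <3.0 and Grade 4 = <2.5 mmol/L. This restores the row already printed. It changes one short set of bullets and costs nothing in trial conduct.

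**Calcium (SAP 9.4).** Settle the open note with the laboratory before database lock.

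- If albumin or corrected calcium is supplied, say so, state who applies the correction, and print the formula.
- If not, mark calcium as not graded by CTCAE, as section 9.4 already does for bicarbonate and platelets, and report it in the normal-range shift table of SAP 5.12.4. The cost is that calcium has no toxicity grade.

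Two alternatives are weaker. Grading total calcium at cut-points printed for corrected calcium would produce grades that the source row does not support, and could misgrade subjects with abnormal albumin. Adding albumin to the panel would change protocol Table 8, which is more than SAP wording.
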